Appendix A

Case#

Understanding the Impact of Asthma in Academic Achievement, School Attendance, and in the Quality of Life in Middle school aged children Questionnaire**Baseline Measure**

These questions will ask about your child's background and asthma history. In order for this study to be useful for families of children with asthma, it is important that everyone give us accurate answers. IMPACT DC team members will not share or discuss any personal information without your permission.

If you have any questions, please let me know. If not, we can start.

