Demographic information will be obtained by a structured interview; the questionnaire (Appendix A) will be used on both cases and controls: the parent/caregiver will be asked about the child's age, gender, race/ethnicity, insurance type. health care utilization, medications usage, highest level of education of the parent/ caregiver, income of the household, and parental report of school services. Cases will complete an additional 11 questions to determine asthma severity to determine NAEPP score and the Asthma Control Test (ACT) score (Appendix F and G).

We will utilize the child's electronic medical record (Cerner for ED charts and eClinicalWorks for the IMPACT DC charts) to determine insurance type and health care utilization. We will also determine each participant's weight and height from the medical record and will access medical records for the period of time we are collecting report cards for to determine clinical information, such as number of ED visits and hospitalizations over the 14 month period that the report cards cover (August 2015-November 2016).

Reporting of Academic Achievement and School Attendance

At the time of recruitment, families will be given a self-addressed, stamped envelope to send the child's 2013 first term (if available), standardized test score report (if available), and final report card to the research team. All report cards/score reports will be returned to the family via US Mail. Academic achievement, standardized test scores, and school attendance will be recorded from the report cards. All report cards in the DCPS system use the same grading scale..

The Self-Perception Profile

The self-perception profile is a reliable validated 6 question questionnaire for children in grades 6-8 that allows a child to self-evaluate their feelings about their engagement in school and their own school performance.

Reporting of the Quality of Life using the Peds QL 4.0 Form

QOL will be measured using the validated PedsQL 4.0 for children, teens, and parents (Appendices B, C, D, and E). The PedsQL 4.0 has four scales with 23 questions which ascertain physical functioning, emotional functioning, social functioning, and school functioning. A 5-point Likert scale is used in the child self-report and for the parent proxy reports. Items are reverse scored and linearly transformed to a 0 to 100 scale (0=100, 1=75, 2=50, 3=25, and 4=0), so higher scores indicate better QOL.

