****Note to Interviewers:**

- **Bold** scripting is meant to be read to participants.
- *[Italicized in brackets]* scripting is a note for clarification that is not meant to be read aloud.

General Information

Interviewer's Initials _____

Interview Date _____ / _____ / _____ (mm/dd/yy)

Time of Interview Start _____ : _____ *[based on 24-hr clock]*

Patient's Initials _____

Patient's Date of Birth _____ / _____ / _____ (mm/dd/yyyy)

Patient's Gender Male Female

Which grade did your child complete in the last 12 months at school _____

Two best contact phone numbers _____ and _____

Best contact Address _____

Health Care Utilization

Let me ask you about your visits to any hospitals other than Children's National on Michigan Avenue and the Children's National Emergency Room at the United Medical Center:

In the last 12 months, have you been to an Emergency Room other than the Children's Emergency Room at either Children's National or the United Medical Center?

1. No *[Skip to next section]*
 Yes *[go to question 5]*

2. How many times in the last 12 months has (CHILD) been to an Emergency Room other than the Children's Emergency Room at either Children's National or the United Medical Center?
_____ times

3. How many times in the last 12 months has (CHILD) been admitted to a hospital other than Children's National Medical Center for asthma?
_____ times

4. How many times in the last 12 months has (CHILD) been in the PICU (Pediatric Intensive Care Unit) of a hospital other than Children's National Medical Center?

_____ times

Current Medication Use

[Do not read options for types of medicines. Just read question as worded, and then record actual response and classify medication. Do not show pictures or demos/samples of asthma medicines. If name unknown but respondent describes medication, or medication is unknown, write down actual response and classify as "Other".]

5. During the past two days, did [CHILD] take or use any medications including pills, syrups, or inhaled medications?

Yes No [skip to question 6] Don't know [skip to question 7]

If yes:

Which medicines? _____

Asthma Medications:

- Inhaled or nebulized steroid (ex. Pulmicort, Flovent, QVAR, Asmanex)
- Short-acting bronchodilator (ex. albuterol, Ventolin, ProAir, Xopenex)
- Long-acting bronchodilator (ex. salmeterol, formoterol)
- Inhaled steroid/LABA combination (ex. Advair, Symbicort, Dulera)
- Long-acting leukotriene inhibitor (ex. Singulair)

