- Oral Steroid (Prednisone, Prednisolone, Dexamethasone)
- Other: _____

Allergy Medications:

- Antihistamines
- Intranasal Steroid
- Other: _____

Non-asthma/allergy medication:

- _____

Adherence:

6. Does your child take a daily medicine?
 Yes No [Skip to question 7]

What is the name of this medication: _____

Asthma Medications:

- Inhaled or nebulized steroid (ex. Pulmicort, Flovent, QVAR, Asmanex)
- Short-acting bronchodilator (ex. albuterol, Ventolin, ProAir, Xopenex)
- Long-acting bronchodilator (ex. salmeterol, formoterol)
- Inhaled steroid/LABA combination (ex. Advair, Symbicort, Dulera)
- Long-acting leukotriene inhibitor (ex. Singulair)
- Oral Steroid (Prednisone, Prednisolone, Dexamethasone)
- Other: _____

Allergy Medications:

- Antihistamines
- Intranasal Steroid

Other: _____

Non-asthma/allergy medication: _____

Demographic / Family History

Finally, research studies always ask a few questions about your family background.

7. What do you consider [CHILD]'s race to be? [Read options and circle all that apply]

 Black or African-American	 White
 Asian	 American Indian or Alaska Native
 Native Hawaiian/Pacific Islander	 Some other race: _____

1. What do you consider [CHILD]'s ethnicity to be? [Read options]

Hispanic

Non-Hispanic

Other: _____

8. Do any of [CHILD]'s parents, brothers, or sisters have asthma? *[Include those who do and do not live in household.]*

Yes No Don't know

9. How many days of school did your child miss over the last school year due to asthma?

10. Does your child receive any special services at school? What are they?

11. What is the highest grade or school level that you have completed?

Never attended school

Grade 1-11

GED or 12th grade

Some college/technical/vocational training

College graduate

Other: _____

12. Keeping in mind the various possible sources of income for your household, such as a job, supplemental security income (SSI) or disability, social security, public assistance, food stamps, unemployment compensation, and child support, what was the total income during [LAST CALENDAR YEAR] from all sources for everyone in your household? Please point to the answer closest to your total household income.

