[Show categories listed on hand card. Ask for last full calendar year. If the respondent cannot give a figure, go over each source of income and get an estimate per month and multiply by twelve]

 \$5,000 or less	 \$5,001 - \$10,000	 \$10,001 - \$20,000
 \$20,001 - \$30,000	 \$30,001 - \$40,000	 \$40,001 - \$50,000
 \$50,001 - \$60,000	 \$60,001 - \$70,000	 \$70,001 - \$80,000
 \$80,001 - \$90,000	 \$90,001 - \$100,000	 \$100,001 - \$150,000
 \$150,001 - \$200,000	 \$200,001 - \$250,000	 \$250,001 or greater
 Refused	 Don't know	

Thank you very much for answering all of my questions. Your answers will help us improve care for children with asthma. As we discussed earlier, you will be compensated with a \$25 gift card after mailing us your child's report card.

[Caregiver given copy of informed consent document]

Time of Interview End _____ : _____ *[based on 24-hr clock]*

Interviewer Comments

Please indicate if respondent had difficulty answering any of the questions, you feel they provided inaccurate or misleading responses, there were any unusual circumstances at the time of the interview, or the respondent had a language or literacy problem. Please reference specific questions if appropriate.

Chart Review

[To be completed after visit in IMPACT DC Asthma Clinic is completed]

From IMPACT DC Clinic Form:

13. Final Asthma Classification [based on clinician's assessment]

- Intermittent
- Mild Persistent
- Moderate Persistent
- Severe Persistent

14. Insurance type

12a. Name of child's insurance provider: _____

12b. Insurance type:

- Public
- Private
- None
- Unknown

15. Zip code of residence: _____

16. Oral Steroids: How many courses of oral steroids in the prior 12 months: _____

17. If applicable: If a patient is already using an ICS, what was the number of puffs displayed on the back of the inhaler they are currently using?
_____ of puffs

From Medical Records:

Health Care Utilization [*from medical records, visits to Children's Hospital or any of the Goldberg Center Children's Health Centers*]:

Emergency Department visits for asthma

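### Appendix A frames the study around asthma for both groups, while quality of life and self-perception are rated by families who know the child's asthma status, with no stated questionnaire order or other guard against reporting bias

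*Combined protocol and SAP*

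**What the plan says.** Section D (Demographic Data for Cases and Controls) states that "the questionnaire (Appendix A) will be used on both cases and controls", with the parent or caregiver as respondent. Section D also requires that controls have no history of asthma.

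Appendix A carries the printed title "Understanding the Impact of Asthma in Academic Achievement, School Attendance, and in the Quality of Life in Middle school aged children". The introduction under it begins "These questions will ask about your child's background and asthma history. In order for this study to be useful for families of children with asthma". The interview ends with "Your answers will help us improve care for children with asthma". Question 9 asks "How many days of school did your child miss over the last school year due to asthma" and has no skip for controls. The interviewer note says that bold "scripting is meant to be read to participants".

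On outcomes, Section D says "QOL will be measured using the validated PedsQL 4.0 for children, teens, and parents", and "A 5-point Likert scale is used in the child self-report and for the parent proxy reports". The Self-Perception Profile is a six-question self-evaluation for grades 6-8. Cases also complete the asthma severity and control forms (Appendices F and G).

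The closing paragraph of Section A makes the association of asthma with QOL one of the study's objectives. Specific Aim 1 and the sample size concern GPA only. GPA, test scores and attendance are recorded from school documents.

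**The concern.** A rating scale compared between two groups is only as good as the assumption that both groups use it in the same way. Here every rater knows the child's group, which a case-control comparison of this kind cannot avoid. What can be avoided is adding asthma cues to the questionnaires around the ratings.

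A case parent who has just recalled absences due to asthma may then judge the PedsQL items on missed school with asthma in mind. A control parent has no such absences to recall. That could lower case scores relative to control scores without any true difference in QOL. The same could apply to self-perception if the child is exposed to the asthma material. At stake is the QOL and self-perception comparison, not the primary GPA question.

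**Working it through.** The plan gives no QOL effect size, standard deviation or power, so there is no figure of its own to reproduce. The check is mainly textual, followed by scale arithmetic under labelled assumptions.

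**1. Exposure to asthma wording.** Both groups receive Appendix A (Section D). The opening and closing speak to the respondent about asthma. Question 9 applies to controls as printed. Question 3 (admissions elsewhere for asthma) also sits in the shared form. However, the routing at question 1 sends a No to the next section and a Yes to question 5, so question 3 is bypassed for everyone.

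**2. Outcome raters.** The PedsQL is completed by child or teen and by parent. The Self-Perception Profile is completed by the child. Neither has an objective component.

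**3. Overlap in content.** The PedsQL has 8 + 5 + 5 + 5 = 23 items. Two of the five school items concern missing school, for feeling unwell and for medical visits. Question 9 asks about missed school too. The overlap is in subject, not in recall window: question 9 covers the last school year, the PedsQL the past month.

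**4. Order.** No section states it.
- Appendix A is labelled a baseline measure and comes before the PedsQL (Appendices B onward).
- Appendices F and G come after the PedsQL by letter.
- The Self-Perception Profile is in none of the appendices supplied.

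Letters are labels, not a schedule, so the order is simply unspecified.

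**5. Scale arithmetic.** Section D gives a step of 25 points per item category. Assume that a scale score is the mean of its items, and that a respondent moves one category on both missed-school items:
- school scale: 2 × 25 / 5 = 10 points for that respondent;
- 23-item total: 2 × 25 / 23 = 2.2 points.

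If a fraction f of case respondents did this and no controls did (assumption), the group means would shift as follows:

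| f | School scale (10 × f) | Total (50/23 × f) |
|---|---|---|
| 0.10 | 1.0 | 0.2 |
| 0.25 | 2.5 | 0.5 |
| 0.50 | 5.0 | 1.1 |

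**6. Consequence for a test.** Let b be a reporting shift in SD units, with n per group and no true difference. With m = b / √(2/n), the false-positive rate of a two-sided 5% test is 1 − Φ(1.96 − m) + Φ(−1.96 − m). For n = 60 (the planned expansion) and b = 0.2, m = 0.2 / √(2/60) = 1.095 and the rate is 19.5%.

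| b (assumed) | n = 60 | n = 30 (assumed, if many forms are incomplete) |
|---|---|---|
| 0 | 5.0% | 5.0% |
| 0.1 | 8.5% | 6.7% |
| 0.2 | 19.5% | 12.1% |
| 0.3 | 37.6% | 21.3% |

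Steps 5 and 6 cannot be joined, because the documents give no SD to convert points into b. They show how sensitive the comparison would be, not how large the bias is.

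**The case against.** The strongest reply is that little of this can be changed. Families know the child's diagnosis, guardians are informed about the study before consenting (Section F), and the PedsQL forms are generic and never mention asthma. QOL lies outside Specific Aim 1 and the sample-size basis. All of that stands. It limits what a fix can achieve and keeps the point minor.

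A reader might also infer that the script announces asthma's effect on schooling and QOL, so that respondents rate knowing the hypothesis. The documents do not support this. The introduction and closing mention neither schooling nor QOL. Only the printed title does, and nothing shows that it is read aloud, since bold type is not reliably preserved in the available text. Neither title nor script says that children with asthma are expected to do worse, and the stated hypothesis concerns school performance.

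Three further inferences fail:
- **That the child hears the script.** Appendix A is a caregiver interview, and no section says the child is present for it.
- **That the asthma material comes just before the ratings.** The order is not given, and Appendices F and G follow the PedsQL by letter.
- **That controls are told the study is not about them and so answer or return cards less carefully.** No text says so. The introduction asks everyone for accurate answers, and careless answering would have no determined direction.

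What survives is the shared asthma framing, question 9 put to controls, and the absence of any stated order or safeguard for outcomes that are wholly subjective.

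**Conclusion.** The concern holds in a limited form. Appendix A gives both groups an asthma-framed interview, raters know the child's status, and the protocol states nothing to limit differential reporting of QOL and self-perception. A shift towards worse case scores is the more plausible direction, but that is a judgement and not shown by the documents.

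The size is not derivable. The point shifts rest on an assumed one-category move, assumed fractions and mean scoring. The false-positive rates rest on assumed shifts of 0.1 to 0.3 SD. None should be quoted as an estimate of bias.

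GPA and attendance come from report cards and are not affected by this route. It would be wrong to read the point as undermining Specific Aim 1. It is a minor weakness that is cheap to reduce.

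**What to change.** - State in Section D that the PedsQL and the Self-Perception Profile are completed first in both groups, before Appendix A and before Appendices F and G.
- Replace the title, introduction and closing of Appendix A with neutral text common to both groups, for example describing a study of children's health and schooling.
- Move questions 9 and 3 to the case-only forms. Controls have no asthma history, so nothing is lost by not asking them. The move also allows the routing that bypasses question 3 to be corrected.
- If data are already collected, report the order actually used and state the limitation alongside the QOL and self-perception results. The document is dated June 2018 and recruitment was planned to end in November 2016, so this may be the step that applies.

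The cost is a wording amendment and a reordering of forms, with no added participants, visits or staff. Consent will presumably still name asthma and families still know the diagnosis, so priming would be reduced and not removed.

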****Note to Interviewers:**

- **Bold** scripting is meant to be read to participants.
- *[Italicized in brackets]* scripting is a note for clarification that is not meant to be read aloud.

General Information

Interviewer's Initials _____

Interview Date _____ / _____ / _____ (mm/dd/yy)

Time of Interview Start _____ : _____ *[based on 24-hr clock]*

Patient's Initials _____

Patient's Date of Birth _____ / _____ / _____ (mm/dd/yyyy)

Patient's Gender Male Female

Which grade did your child complete in the last 12 months at school _____

Two best contact phone numbers _____ and _____

Best contact Address _____

Health Care Utilization

Let me ask you about your visits to any hospitals other than Children's National on Michigan Avenue and the Children's National Emergency Room at the United Medical Center:

In the last 12 months, have you been to an Emergency Room other than the Children's Emergency Room at either Children's National or the United Medical Center?

1. No *[Skip to next section]*
 Yes *[go to question 5]*

2. How many times in the last 12 months has (CHILD) been to an Emergency Room other than the Children's Emergency Room at either Children's National or the United Medical Center?
_____ times

3. How many times in the last 12 months has (CHILD) been admitted to a hospital other than Children's National Medical Center for asthma?
_____ times

4. How many times in the last 12 months has (CHILD) been in the PICU (Pediatric Intensive Care Unit) of a hospital other than Children's National Medical Center?

_____ times

Current Medication Use

[Do not read options for types of medicines. Just read question as worded, and then record actual response and classify medication. Do not show pictures or demos/samples of asthma medicines. If name unknown but respondent describes medication, or medication is unknown, write down actual response and classify as "Other".]

5. During the past two days, did [CHILD] take or use any medications including pills, syrups, or inhaled medications?

Yes No [skip to question 6] Don't know [skip to question 7]

If yes:

Which medicines? _____

Asthma Medications:

- Inhaled or nebulized steroid (ex. Pulmicort, Flovent, QVAR, Asmanex)
- Short-acting bronchodilator (ex. albuterol, Ventolin, ProAir, Xopenex)
- Long-acting bronchodilator (ex. salmeterol, formoterol)
- Inhaled steroid/LABA combination (ex. Advair, Symbicort, Dulera)
- Long-acting leukotriene inhibitor (ex. Singulair)
- Oral Steroid (Prednisone, Prednisolone, Dexamethasone)
- Other: _____

Allergy Medications:

- Antihistamines
- Intranasal Steroid
- Other: _____

Non-asthma/allergy medication:

- _____

Adherence:

6. Does your child take a daily medicine?
 Yes No [Skip to question 7]

What is the name of this medication: _____

Asthma Medications:

- Inhaled or nebulized steroid (ex. Pulmicort, Flovent, QVAR, Asmanex)
- Short-acting bronchodilator (ex. albuterol, Ventolin, ProAir, Xopenex)
- Long-acting bronchodilator (ex. salmeterol, formoterol)
- Inhaled steroid/LABA combination (ex. Advair, Symbicort, Dulera)
- Long-acting leukotriene inhibitor (ex. Singulair)
- Oral Steroid (Prednisone, Prednisolone, Dexamethasone)
- Other: _____

Allergy Medications:

- Antihistamines
- Intranasal Steroid

Other: _____

Non-asthma/allergy medication: _____

Demographic / Family History

Finally, research studies always ask a few questions about your family background.

7. What do you consider [CHILD]'s race to be? [Read options and circle all that apply]

 Black or African-American	 White
 Asian	 American Indian or Alaska Native
 Native Hawaiian/Pacific Islander	 Some other race: _____

1. What do you consider [CHILD]'s ethnicity to be? [Read options]

Hispanic

Non-Hispanic

Other: _____

8. Do any of [CHILD]'s parents, brothers, or sisters have asthma? *[Include those who do and do not live in household.]*

Yes No Don't know

9. How many days of school did your child miss over the last school year due to asthma?

10. Does your child receive any special services at school? What are they?

11. What is the highest grade or school level that you have completed?

Never attended school

Grade 1-11

GED or 12th grade

Some college/technical/vocational training

College graduate

Other: _____

12. Keeping in mind the various possible sources of income for your household, such as a job, supplemental security income (SSI) or disability, social security, public assistance, food stamps, unemployment compensation, and child support, what was the total income during [LAST CALENDAR YEAR] from all sources for everyone in your household? Please point to the answer closest to your total household income.

[Show categories listed on hand card. Ask for last full calendar year. If the respondent cannot give a figure, go over each source of income and get an estimate per month and multiply by twelve]

 \$5,000 or less	 \$5,001 - \$10,000	 \$10,001 - \$20,000
 \$20,001 - \$30,000	 \$30,001 - \$40,000	 \$40,001 - \$50,000
 \$50,001 - \$60,000	 \$60,001 - \$70,000	 \$70,001 - \$80,000
 \$80,001 - \$90,000	 \$90,001 - \$100,000	 \$100,001 - \$150,000
 \$150,001 - \$200,000	 \$200,001 - \$250,000	 \$250,001 or greater
 Refused	 Don't know	

Thank you very much for answering all of my questions. Your answers will help us improve care for children with asthma. As we discussed earlier, you will be compensated with a \$25 gift card after mailing us your child's report card.

[Caregiver given copy of informed consent document]

Time of Interview End _____ : _____ *[based on 24-hr clock]*

Interviewer Comments

Please indicate if respondent had difficulty answering any of the questions, you feel they provided inaccurate or misleading responses, there were any unusual circumstances at the time of the interview, or the respondent had a language or literacy problem. Please reference specific questions if appropriate.

Chart Review

[To be completed after visit in IMPACT DC Asthma Clinic is completed]

From IMPACT DC Clinic Form:

13. Final Asthma Classification [based on clinician's assessment]

- Intermittent
- Mild Persistent
- Moderate Persistent
- Severe Persistent

14. Insurance type

12a. Name of child's insurance provider: _____

12b. Insurance type:

- Public
- Private
- None
- Unknown

15. Zip code of residence: _____

16. Oral Steroids: How many courses of oral steroids in the prior 12 months: _____

17. If applicable: If a patient is already using an ICS, what was the number of puffs displayed on the back of the inhaler they are currently using?
_____ of puffs

From Medical Records:

Health Care Utilization [*from medical records, visits to Children's Hospital or any of the Goldberg Center Children's Health Centers*]:

Emergency Department visits for asthma

18. Number of ED visits in prior 12 months: _____

19. Hospitalizations for asthma _____

20. Number of hospitalizations in prior 12 months: _____

21. PICU Admissions

Number of PICU admissions in the last 12 months: _____

21. Urgent care visits for asthma (if Goldberg Center patient)

Number of urgent care visits in prior 12 months: _____

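### As printed, both answers to Appendix A question 1 lead to question 5, so questions 2 to 4 on care at other hospitals are bypassed (minor); separately, question 9 counts asthma absences only and tells us nothing about controls

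*Combined protocol and SAP*

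**What the plan says.** Section D (Demographic Data for Cases and Controls) says that "the questionnaire (Appendix A) will be used on both cases and controls". The topics it lists for the caregiver include "health care utilization, medications usage, highest level of education of the parent/ caregiver". The same section also takes utilization from the electronic medical record.

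In Appendix A, Health Care Utilization, question 1 asks about emergency visits at other hospitals in the past 12 months. No carries the instruction "Skip to next section"; Yes carries "go to question 5". Question 2 counts outside emergency visits. Question 3 counts how often the child has "been admitted to a hospital other than Children's National Medical Center for asthma". Question 4 counts outside intensive-care stays. Question 5 opens the following section, Current Medication Use.

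The Chart Review part of Appendix A limits its utilization counts to data "from medical records, visits to Children's Hospital or any of the Goldberg Center Children's Health Centers".

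On absence, Appendix A question 9 reads: "How many days of school did your child miss over the last school year due to asthma". Section D (Reporting of Academic Achievement and School Attendance) names a different source: "Academic achievement, standardized test scores, and school attendance will be recorded from the report cards". Section E (Sample Size) expects fewer than half of the participants to return their final report cards.

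**The concern.** A skip instruction should separate respondents who need the follow-up questions from those who do not. Here both answers arrive at the same item, so the three count questions belong to no route. An interviewer who obeys the form records only whether any outside emergency visit took place. Utilization is a stated interview variable for both groups, and the record review cannot see other hospitals. Two misreadings could follow at analysis: blanks in questions 2 to 4 taken as zeros, and own-site counts taken as total utilization.

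Question 9 is a separate and weaker matter. Attendance is one of the two outcomes that Section D sets out to compare between children with and without asthma. The form asks every caregiver about absence, but in a way that can yield a meaningful number only for cases.

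**Working it through.** The documents give no figure for this point, so there is none to reproduce. The check is a trace of the printed routing, followed by a look at other possible sources.

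**Routing as printed (Appendix A)**

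| Answer to Q1 | Instruction leads to | Items asked | Q2–Q4 asked? |
|---|---|---|---|
| No | next section, first item Q5 | Q1, Q5 | no |
| Yes | Q5 | Q1, Q5 | no |

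Questions 2 to 4 are reached on 0 of 2 routes, so 3 of the 4 outside-care items are bypassed. Question 5 asks about medicines taken in the past two days and is not a utilization count. Its own skips, to questions 6 and 7, agree with the numbering that follows, so the printed target of question 1 really is the medication item.

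**Routing after repair**

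- Yes sent to Q2: Yes gives Q1, Q2, Q3, Q4, Q5; No gives Q1, Q5. All three counts are obtained from Yes respondents. A child admitted elsewhere without an outside emergency visit is still missed.
- No also sent to Q3: No gives Q1, Q3, Q4, Q5, which closes that gap.

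**Could another source supply the counts?** The chart review is confined to the hospital and its own health centers. The electronic records named in Section D are the hospital's emergency department and asthma clinic charts. Neither is planned to capture visits elsewhere.

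**Limit within question 3.** It counts only admissions for asthma. Controls have no history of asthma (Section D), so even when asked it is zero or not applicable for them.

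**Question 9**

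- Controls, by definition, can answer only zero or not applicable.
- For cases it gives asthma-related days, not total absence.
- Report cards: with under 50% returned, the expansion yields fewer than 0.50 × 120 = 60 cards. More than 120 − 60 = 60 children would then have no attendance record from a card. This is expansion only; the original cohort's size and returns are not given.
- For those children, question 9 gives no all-cause absence count in either group. The two PedsQL school items on missed school (Appendices B to D and the teen report) are frequency ratings over the past month, not day counts.
- Question 9 does not name its school year, and interviews were planned for May to November 2016. That window may span the end of one school year and the start of the next, so answers could refer to different years.

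**Appendix F, question 3 (editorial).** The stem asks about quick-relief medicine at night, but the answer options count days per week and uses per day.

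**The case against.** The strongest reply is that the skip target is a misprint that any interviewer would see through. Someone who has just recorded Yes finds three count questions on the same topic directly below, with blanks to fill. The form has other numbering slips: an ethnicity item numbered 1 after question 7, sub-items 12a and 12b under item 14, and two items numbered 21. Nothing planned depends on questions 2 to 4: no aim or analysis names outside utilization, and the hospital's own records still supply the main utilization data. All of this stands. A reader might infer that the outside counts were lost. The documents do not support that; they show only what the form instructs, not what interviewers did.

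On question 9, the reply is that the plan never asks it to measure attendance in both groups, and that days lost to asthma is a sensible burden item for cases. That also stands. A reader might infer that question 9 is a design error, or that it leaves the attendance comparison underpowered. Neither follows. The plan assigns attendance to report cards and proposes no case-control comparison of question 9. Any loss of precision in attendance comes from low card return and would be the same if question 9 were absent.

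What survives is that the printed instruction is wrong, no other planned source fills the gap, and correcting it costs almost nothing.

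**Conclusion.** Minor, but wrong as written. If the form is followed literally, questions 2 to 4 are never asked of anyone, and outside care is reduced to a single yes/no about emergency visits. The trace is certain. The consequence is not: actual data loss is unknown and may be nil. The effect is confined to outside-hospital utilization, and the grade point average comparison is untouched.

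Question 9 is an opportunity for a cheap improvement and not an error. It is uninformative in controls, so the existing answers should not be compared between groups. An all-cause version would give a secondary attendance measure for families whose cards do not come back. This rests on the plan's own expectation of under 50% return.

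The Appendix F mismatch is editorial; no effect on severity or control classification is claimed.

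**What to change.** **Interviews already done.** These are probably all of them, since recruitment was planned to end in November 2016 and the document is dated June 2018.

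- Report how often questions 2 to 4 were completed, by group and by the answer to question 1.
- Do not treat blanks as zeros, or own-site counts as total utilization.
- Do not compare the existing question 9 between cases and controls.

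This costs one tabulation. Counts never taken cannot be recovered from the planned chart review.

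**Any further interviews.**

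- Send Yes on question 1 to question 2. Optionally send No to question 3, so that outside admissions and intensive-care stays without an outside emergency visit are captured. The cost is one or two skip targets and, under the option, two more questions for caregivers who answer No.
- Reword question 9 to total school days missed for any reason in the 2015–2016 school year (to date, if that year is still running), with a follow-up for cases on days due to asthma. Use it in both groups as a secondary, caregiver-reported measure alongside report cards. The downsides are recall error and no comparability with interviews on the old form.
- Reconcile the stem of Appendix F question 3 with its answer options.
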